### **Data analysis**

**Consideration of Relevant Biological and Sociological Variables:** Participants in both groups will be compared on potentially confounding baseline variables (age, gender, socio-economic status, education, fitness, co-morbidities, degree of hemiplegia, location/type of stroke, side of lesion) to assess the extent of any imbalances across groups. Baseline variables in which there is a clinically important difference between groups may be included as covariates. Participants will also be compared using participation and adherence metrics. While recent evidence has shown that genetic polymorphisms may influence motor recovery following stroke, it is beyond the scope of this project due to cost and lack of expertise to consider these as covariates.

**Analysis of Motor Outcomes (Aim 1):** Motor outcomes for each group will be compared at baseline, mid-treatment, EOT, and EOT+4. The group effect on ARAT, FMA, and WMFT will be estimated using separate linear mixed effects models with a random effect for subject, fixed effects for group, examination time, and baseline value of the outcome. An appropriate covariance structure (e.g.: unstructured, compound symmetric, autoregressive) will be used as determined using Akaike's information criterion. The effects of group, time, and the group-by-time interaction will be assessed for each outcome. To adjust for multiple comparisons, the family-wise error rate will be controlled via Bonferroni-type adjustment required for multiple comparisons. Tukey's and other post-hoc comparisons will be used to explore pairwise differences in main effects of group membership. To further investigate the effect of the intervention group assignment on the various sub-scales of the ARAT, a multivariate analysis of variance will be used along with a separate principle component analysis to study if further dimension reduction is possible in using these two tests in the study. Transformations of the data will be made to achieve normality or other model assumptions. The overall alpha level will be set at 0.05.

**Bimanual dexterity data:** All force and torque data will be filtered with a phase-symmetric low-pass filter using Woltring's algorithm with existing Matlab programs. The primary kinetic and kinematic outcomes will be: coordination of grip-load coupling, time delay between grasping force initiation for each limb, overall time to task completion and rate of grip force production for each limb.

**Cost-Effectiveness Analysis (Aim 2):** A decision analytic model using a systematic, quantitative approach using Treeage Pro® will be developed comparing AE+RTP and UE RTP only. All possible outcomes will be incorporated into the model. A hospital/payer perspective will be adopted and include all relevant costs and outcomes. All outcome probabilities used in the model will be determined from the clinical trial's data collection at the 6 time points. As part of my training, I will learn cost-effectiveness methodologies, including approaches to analyze variability and uncertainty in the model and the population, and methods to evaluate model generalizability (sensitivity analysis) in accordance with current recommendations. For this analysis, a cost effectiveness summary will be produced, including the costs and effects of each intervention, the cost-effectiveness ratio of the interventions, and the incremental cost-effectiveness ratio between the interventions from two perspectives: healthcare sector and society. Deterministic and probabilistic sensitivity analyses will be used to evaluate result uncertainty attributable to the model and population variability. Sensitivity analyses will be summarized to show that the optimal strategy is the choice strategy in 'what' percentage of time and for 'what' variable values and be reported as a cost-effectiveness acceptability curve.

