
### **Approach**

**The proposed project determining the clinical effectiveness of AE in facilitating motor recovery and determining the cost-effective strategy could fundamentally alter current rehabilitation approaches and drive the adoption of AE into stroke rehabilitation.**

**Experimental Overview:** A prospective, single-center, parallel group, rater-blind clinical trial is proposed. A schematic depicting workflow and outcomes is provided in Figure 2. A total of 60 individuals with chronic

stroke (>6 months) will be randomized to one of two time-matched groups: 1) AE and RTP or 2) RTP only. All groups receive an identical dose of contact time (36 hours) over a course of 8 weeks (3X per week). Upper extremity motor outcomes (Aim 1) will be collected at baseline, mid-treatment, end of treatment (EOT), and EOT+4 weeks. Data concerning participant demographics, social determinants, and intervention resource utilization (including personnel) will be collected during the clinical trial and at 6-months (primary outcome on full data set, Aim 2) and 12-months follow-up (secondary outcome on subset of sample, Aim 2).

**The following elements of our experimental design ensure scientific rigor:** 1) Randomization stratified according to baseline function and age; 2) Blinding of the rater; 3) Utilization of a time-matched control group; 4) Sample size justified to demonstrate group differences based on preliminary studies; and 5) Sound statistical analysis plan. An intent-to-treat approach will be used to address any missing data; to date <1% of data in our preliminary studies are missing.

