### **Power and Sample Size Justification:**

The power and sample size calculation is based on FMA scores from our R03 study. A minimal clinically important difference (MCID) range of 4.25-7.25 points has been reported for the FMA with baseline subject standard deviation of 5.7 – 6.3 points. To be conservative, we have assumed the MCID to be 4.25 for the purposes of our power calculations. Based on results from our R03 which included 3 intervention groups, the forced AE+RTP group, voluntary AE+RTP group, and RTP only groups improved on the FMA by a mean of 12.33(4.13), 4.83(4.91), and 4.4(4.87), respectively. In the sample size and power computation, it is assumed that there is an increase of 2\*MCID for the AE+RTP group and 1\*MCID for the RTP only group, along with

statistically significant differences between the groups at EOT. Further, it is assumed that subject SD will remain ~10 points within the group. Based on these assumptions, with n=30 in each of the intervention groups, we will have a .87 power at the 0.05 significance level to detect pairwise group differences equivalent to an effect size of .4. All computations were completed using the PASS 13 program (East Kaysville, Utah).

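### Covariates for the Aim 1 models may be added at discretion according to observed baseline imbalance, with no cut-off, timing or primary model stated, so control at 0.05 is not guaranteed

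*Combined protocol and SAP*

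**What the plan says.** All references are to the combined protocol and SAP.

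- **Data analysis, paragraph on biological and sociological variables.** The arms are compared on nine items: "age, gender, socio-economic status, education, fitness, co-morbidities, degree of hemiplegia, location/type of stroke, side of lesion". The rule follows: "Baseline variables in which there is a clinically important difference between groups may be included as covariates". The sentence does not name Aim 1, but it stands directly above the Aim 1 models in the same section.
- **Data analysis, Analysis of Motor Outcomes (Aim 1).** The core mixed model has a random subject effect and "fixed effects for group, examination time, and baseline value of the outcome". Multiplicity is handled as follows: "the family-wise error rate will be controlled via Bonferroni-type adjustment required for multiple comparisons". Then: "The overall alpha level will be set at 0.05".
- **Approach, Experimental Overview.** The design features include "Randomization stratified according to baseline function and age". Blinding is described as "A prospective, single-center, parallel group, rater-blind clinical trial is proposed". No blinding of the analyst is stated.
- **Power and Sample Size Justification.** The calculation is made "with n=30 in each of the intervention groups".

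No section gives a cut-off for an important imbalance, says whether the covariate decision comes before outcome data are seen, or names the primary model. The Bonferroni-type adjustment is not said to cover a choice among covariate sets.

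**The concern.** In a randomized trial, baseline differences between arms arise by chance. An observed difference says nothing about how strongly a variable predicts the outcome, so it is a poor reason to adjust. Because inclusion is optional, the same data can support several analyses of ARAT and FMA, and a reader of the results could not tell whether the reported model was settled before or after the outcomes were seen.

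Two things are at stake. First, the 0.05 level is not a property of an open procedure. Second, the rule tends to pick the wrong variables. Age was judged important enough to stratify on, yet it is not in the core model. It would enter only if it were imbalanced, which stratification is meant to prevent, while a weakly prognostic variable could enter by chance.

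**Working it through.** **Inputs from the document:** 30 per arm, nine candidate variables, an optional rule triggered by imbalance, the baseline outcome already in the model, alpha 0.05 (two-sided assumed, since sidedness is not stated).

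**Assumptions, because the document gives no figure:** the imbalance cut-off (0.2 to 0.5 SD) and the share R² of the variance remaining after baseline that the nine variables jointly explain (0 to 0.4).

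**1. How often could the rule apply?** For a continuous variable under simple randomization, the SD of a standardized difference is √(2/30) = 0.258.

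- Cut-off 0.25 SD: P(|d| > 0.25) = 0.333. At least one of nine: 1 − (1 − 0.333)⁹ = 0.97.
- Cut-off 0.5 SD: P(|d| > 0.5) = 0.053. At least one of nine: 1 − (1 − 0.053)⁹ = 0.39.
- Removing age and degree of hemiplegia, which stratification should help to balance, leaves seven: 1 − 0.667⁷ = 0.94 and 1 − 0.947⁷ = 0.32.

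**2. Type I error.** Trials were simulated under no group effect with 30 per arm and a baseline slope of 0.7. The analysis was ANCOVA on the baseline value, which with complete data and compound symmetry corresponds to the mixed model's group main effect. There were 10,000 trials per row, so the Monte Carlo standard error is about 0.002.

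| R² | Baseline only | Baseline + all nine | Flagged variables added mechanically (cut-off 0.2 / 0.3 / 0.5) | Smaller p of the two models (0.2 / 0.3 / 0.5) | Best of all subsets of flagged variables (0.3 / 0.5) |
|---|---|---|---|---|---|
| 0 | 0.050 | 0.046 | 0.047 / 0.049 / 0.048 | 0.064 / 0.063 / 0.055 | 0.076 / 0.056 |
| 0.2 | 0.050 | 0.051 | 0.041 / 0.041 / 0.047 | 0.068 / 0.065 / 0.058 | 0.090 / 0.061 |
| 0.4 | 0.049 | 0.046 | 0.027 / 0.029 / 0.040 | 0.063 / 0.062 / 0.057 | 0.095 / 0.060 |

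Both fixed-covariate analyses reproduce the stated 0.05, so any departure comes from the selection.

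Two variations agree:

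- Correlated covariates (0.2), three of them binary, R² = 0.3, cut-offs 0.3 and 0.5: fixed sets 0.049-0.052, mechanical 0.040-0.044, smaller of two p-values 0.059-0.076.
- Nine independent covariates with coefficients of 0.1 or 0.2 SD (9 × 0.01 = 9% to 9 × 0.04 = 36% of residual variance), cut-offs 0.25 and 0.5: fixed 4.9-5.3%, mechanical 3.5-4.8%, smaller of two 5.5-7.0%, best of all flagged-variable models 5.7-9.9%.

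The mechanical rule is conservative for a simple reason. When imbalance is large, the adjusted test is valid. When imbalance is small, the variable is left in the error term, so the reported standard error is too large.

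**3. Leaving out age.** The same mechanism applies to a balanced stratification factor that is not modelled. If age explained a share r of the remaining variance and were perfectly balanced, the reported standard error would be too large by 1/√(1 − r), and the test would in effect use a critical value of 1.96/√(1 − r).

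- r = 0.04 (one covariate at 0.2 SD): standard error 1.02 times too large; 1.96/√0.96 = 2.00; actual level about 0.046.
- r = 0.20 (an extreme case for age alone): standard error 1.12 times too large; 1.96/√0.80 = 2.19; actual level about 0.028.

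Real stratification balances age only within its categories, so these are upper limits on the effect at each r.

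**The case against.** The strongest reply is that the stated trigger is baseline data, not outcomes. A reader might infer that choosing covariates after seeing which variables differ makes the group test exceed 0.05. The document does not support that: selection on baseline imbalance alone leaves the error at or below 5% in every setting tried. The figures above 5% need an analyst who fits several models, looks at the outcome results and picks one. The plan does not describe that step. This objection stands, and it limits the point to a lack of guarantee.

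It is also fair that the core model already fixes group, time and the baseline outcome, plausibly the strongest predictor; that the candidates are a named list; and that the criterion is clinical importance rather than a significance test. These limit the room for choice without closing it. Items such as co-morbidities, socio-economic status and stroke location or type can each be coded in more than one way.

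A reader might also infer from the 97% figure that the rule will almost always apply. That rests on an assumed 0.25 SD cut-off and on independent, continuous, unstratified variables. At 0.5 SD with two variables removed, it is 32%.

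Finally, a mechanical rule with a stated cut-off, fixed before outcomes are seen, would also hold the error at or below 5%. That is true, but it would still choose variables for the wrong reason and lose sensitivity when they are prognostic.

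**Conclusion.** The point holds as a gap in specification combined with an inferior selection rule. It is not a demonstrated loss of alpha. Under the assumed cut-offs and prognostic strengths, the type I error is about 3-5% if the rule is applied mechanically, about 5.5-7.6% if the better of two models is reported, and up to about 10% with free choice among all subsets. The last is a worst case. Direction and rough size agree across the settings; the exact values depend on assumptions that the document cannot settle, and the simulations ignore stratification.

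The loss from leaving out age needs no misuse of discretion. It is small if age is weakly prognostic and matters more if age is strongly so. The change should be made because it improves the primary analysis at almost no cost.

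**What to change.** Replace the covariate sentence in Data analysis with:

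> The primary Aim 1 models adjust for each outcome's own baseline value and for the stratification factors (baseline function and age), plus any prognostic variable named before outcome data are examined by group. No covariate is added to or dropped from the primary models because of observed imbalance. Models adding imbalanced variables are reported as labelled sensitivity analyses.

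The baseline comparison of the arms can stay as description. The cost is one sentence and a few degrees of freedom among 60 participants. Age and baseline function are already collected, and no visit or sample size changes. The investigator gives up only the freedom to alter the primary model afterwards, and can still report the adjusted models.

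### Does the Aim 1 mixed model use baseline both as a response and as a covariate?

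*Combined protocol and SAP*

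**What the plan says.** Under Data analysis, the paragraph on motor outcomes (Aim 1) opens with "Motor outcomes for each group will be compared at baseline, mid-treatment, EOT, and EOT+4". The next sentence gives the model: "The group effect on ARAT, FMA, and WMFT will be estimated using separate linear mixed effects models", specified as "linear mixed effects models with a random effect for subject, fixed effects for group, examination time, and baseline value of the outcome". On the covariance it says "An appropriate covariance structure (e.g.: unstructured, compound symmetric, autoregressive) will be used", with the choice made by Akaike's criterion. It then states "The effects of group, time, and the group-by-time interaction will be assessed for each outcome", and adds that post-hoc comparisons "will be used to explore pairwise differences in main effects of group membership".

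The four visits are those in the Experimental Overview under Approach, where the upper extremity outcomes "will be collected at baseline, mid-treatment, end of treatment (EOT), and EOT+4 weeks". The Aim 2 paragraph of Data analysis takes its model probabilities from "data collection at the 6 time points". That count agrees with the Experimental Overview if it means the four visits plus the 6- and 12-month follow-ups.

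No sentence defines the levels of examination time in the model, and none says whether the baseline measurement is a response row.

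**The concern.** Read literally, the only list of times in the Aim 1 paragraph includes baseline, and the same paragraph puts the baseline value on the right-hand side of the model. An analyst who loaded four rows per participant and added the covariate would be regressing baseline on itself.

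Three things could then go wrong. The averaged group effect would include a row in which the adjusted difference is zero by construction, and so would be diluted. The baseline residuals would be far smaller than the others, and a common-variance fit would spread that spurious precision over the later visits. With an unstructured covariance the likelihood would have no maximum. Since the plan says that the group effect will be estimated for all three clinical motor scales, a misreported size or an anti-conservative EOT test would matter.

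**Working it through.** The plan prints no figure on this point, so there is none to reproduce; its power figure does not enter. The check asks what the bad coding would do, and then whether the text leads there.

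**Inputs.** 30 per arm, planning difference 4.25 FMA points (8.5 against 4.25), SD about 10, baseline SD 5.7-6.3 and change SDs 4.13, 4.87 and 4.91, all from Power and Sample Size Justification. The within-subject correlation ρ is not given. With equal variances over time, ρ = 1 − SD²(change)/(2·SD²):

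- 1 − 4.91²/(2 × 5.7²) = 0.63 and 1 − 4.13²/(2 × 6.3²) = 0.79 with the baseline SDs
- 0.88 to 0.915 with SD 10

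These SDs may come from different samples, so ρ is taken over 0.5-0.915 as an assumption.

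**1. Averaged group effect, four rows, compound symmetry.** The common slope on baseline is b = (1 + 3ρ)/4. The estimate is (3/4)(mean post-baseline difference) + (1/4)(baseline difference) − b(baseline difference) = (3/4)[mean post-baseline difference − ρ × baseline difference]. That is exactly 3/4 of the three-row estimate. In one simulated data set (ρ 0.79, SD 10) the effect was 3.587 (SE 0.881) with four rows and 4.782 (SE 1.175) with three; t = 4.069 in both. The size shrinks and the test does not move. An effect of 4.25 held constant over all three later visits would be reported as 0.75 × 4.25 = 3.19.

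**2. Baseline-adjusted difference at EOT.** In units of the outcome variance, the residual variance is (1 − b)² at baseline and 1 + b² − 2bρ at each later visit. A compound-symmetry fit averages them, so

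model SE / true SE = √{ [(1 − b)² + 3(1 + b² − 2bρ)] / [4(1 + b² − 2bρ)] }.

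At ρ = 0.7, b = 0.775; the variances are 0.0506 and 0.5156, their average over four rows is 0.3994, and the ratio is √(0.3994/0.5156) = 0.880.

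| ρ | b | ratio | SE too small by |
|---|---|---|---|
| 0.5 | 0.625 | 0.892 | 10.8% |
| 0.7 | 0.775 | 0.880 | 12.0% |
| 0.9 | 0.925 | 0.870 | 13.0% |

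In simulation (20,000 null trials per ρ) the nominal 5% test ran at 8.0-9.4% with four rows and 4.8-5.2% with three.

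**3. Change from baseline (EOT minus baseline, by group).** Here the covariate cancels. Type I error was 5.0-5.3%, and 4.9-5.3% for the overall group-by-time test. The cost is precision only: the SE is √(2/(1 + ρ)) times that of the adjusted difference, 15% larger at ρ 0.5 and 2% at 0.915.

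**4. Unstructured covariance.** As the slope approaches 1 the baseline residual variance goes to 0. With the slope held at 0.7, 0.99, 0.9999 and 0.999999, the four-row log-likelihood in one data set was −694.8, −490.8, −214.5 and +61.9. With three rows it settled at −555.7. Akaike's criterion cannot rank a model whose likelihood keeps rising, and an analyst would probably notice.

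**5. Does the text prescribe four rows?** The opening sentence says when groups are compared; the model is set out in the sentence after it. A baseline comparison is also natural as description: the preceding paragraph of Data analysis already compares the arms on baseline variables to look for imbalance. The count of six time points belongs to the Aim 2 decision model. It shows that baseline is a collection visit, which nobody doubts, and says nothing about the responses in Aim 1. With the three later visits as responses, the usual meaning of a baseline covariate, steps 1 to 4 show no fault.

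**The case for a change.** The best case for a change is that the literal text permits the bad coding. Examination time is undefined, the only list near it includes baseline, and a random subject effect alone already implies compound symmetry, the structure for which the figures hold. The affected estimate is one the plan intends to report for every clinical motor scale, no single contrast is named as primary, and one sentence would close the gap at no cost.

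The arithmetic stands, and so does the observation that the text is silent. The rest carries less weight. Reaching the harm takes a coding that no sentence requests, a breakdown of the unstructured candidate that goes unheeded, and then the reporting of one of the two affected quantities. The effects that the plan lists for testing (group, time and their interaction) do not include the baseline-adjusted EOT contrast, which is the only anti-conservative group test found.

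The drop from 4.25 to 3.19 also needs an effect that is constant over the three later visits, whereas the power section ties the difference to EOT. With effects of 0.2, 0.425 and 0.3 SD at the three visits, the correct averaged effect is 0.925/3 = 0.308 SD, already below the EOT value of 0.425; four rows give 0.925/4 = 0.231. The plan never judges the averaged effect against the minimal clinically important difference. Which contrast is primary is a separate question.

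**Conclusion.** No change follows. The plan leaves unstated that the responses are mid-treatment, EOT and EOT+4, but the baseline covariate makes that the ordinary reading, and under it there is no error. The consequences are conditional on a four-row coding with a compound-symmetry fit: an averaged effect at 3/4 of its size with the same t, and an EOT standard error about 11-13% too small (type I error about 8-9%) for an assumed ρ of about 0.5-0.9. The averaged group test, the change-from-baseline contrast and the group-by-time test hold their level even then. Writing the response visits into the analysis code would be harmless tidiness; the plan does not depend on it.

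### Randomization is stratified by age, but the Aim 1 mixed models have no age term: if age is prognostic, the standard error of the group difference is overstated and a little power is lost (minor)

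*Combined protocol and SAP*

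**What the plan says.** The experimental overview in the Approach section lists "Randomization stratified according to baseline function and age" among the features that ensure rigor. It gives no age cut-points, no measure of baseline function for the strata and no block size. Motor outcomes "will be collected at baseline, mid-treatment, end of treatment (EOT), and EOT+4 weeks".

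Under Analysis of Motor Outcomes (Aim 1), in Data analysis, ARAT, FMA and WMFT each get a linear mixed model with a random subject effect and "fixed effects for group, examination time, and baseline value of the outcome". The plan adds that "The effects of group, time, and the group-by-time interaction will be assessed for each outcome" and does not say which of these effects decides Aim 1.

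Age heads the list of baseline variables to be compared between groups. It can enter the models only through this rule: "Baseline variables in which there is a clinically important difference between groups may be included as covariates". No threshold is given.

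The Power and Sample Size Justification section assumes "statistically significant differences between the groups at EOT" and states that, with 30 per group, "we will have a .87 power at the 0.05 significance level".

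**The concern.** Stratifying on a prognostic factor removes chance imbalance in that factor, which lowers the true sampling variance of the group difference. A model that omits the factor leaves its variance in the residual and computes the standard error as if the imbalance could still have occurred. The reported standard error is then too large, the confidence interval too wide and the test conservative. There is no bias and no inflation of type I error. What is at stake is a small amount of power in a trial of 60.

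The covariate rule does not close the gap. It is discretionary and responds to observed imbalance, whereas the loss here comes from balance that the model fails to credit. Stratification also makes the rule unlikely to be met for age.

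**Working it through.** **Inputs from the documents.** 60 participants, 30 per group; alpha .05 (two-sided assumed); stratification by baseline function and age; model terms as quoted; three post-baseline visits; stated power .87.

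**Assumed, because the documents do not give them.** Partial correlation r between age and outcome, given baseline: .2, .3 or .4. Strata: age and baseline function each cut at the median (2x2), permuted blocks of 4. Baseline-outcome correlation .7; residual correlation between visits .7.

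**The plan's own figure.** The .87 is recovered if the stated effect size of .4 is read as Cohen's f, that is d = .8. The standard error is √(2/30) = .258, and .8/.258 = 3.098. Power is then Φ(3.098 − 1.96) = .873, or .861 with the exact t. The power comparisons below therefore start near .87.

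**Closed form, one visit.** Set the residual variance given baseline to 1.

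- Model-SE ratio, without age to with continuous age: 1/√(1 − r²) = 1.021, 1.048, 1.091.
- A normally distributed age cut at its median keeps 1 − 2/π = .363 of its variance within the halves. With the halves balanced, the true variance without an age term is proportional to 1 − r² + .363r². The true-SD ratio is √[(1 − r² + .363r²)/(1 − r²)] = 1.008, 1.018, 1.034.
- The model SE without age therefore exceeds its own true SD by 1/√(1 − r² + .363r²) = 1.013, 1.030, 1.055. By the normal approximation, the nominal 5% test has size 4.7%, 4.4%, 3.9%.

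**Simulation.** 40,000 trials per r; random-intercept model with group, time, group-by-time and baseline, with or without continuous age. Effects were set to give power near .87 without age: .81 residual SD at EOT, and .81 × √((1 + 2 × .7)/3) = .72 for the three-visit average.

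| Group difference | r | Model-SE ratio | True-SD ratio | Power without → with age |
|---|---|---|---|---|
| EOT | .2 | 1.018 | 1.006 | .874 → .882 |
| EOT | .3 | 1.046 | 1.018 | .879 → .901 |
| EOT | .4 | 1.089 | 1.034 | .881 → .917 |
| Average | .2 | 1.022 | 1.007 | .867 → .878 |
| Average | .3 | 1.057 | 1.022 | .868 → .895 |
| Average | .4 | 1.110 | 1.042 | .866 → .914 |

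Type I error at EOT is .048, .045, .040 without age and .050, .050, .051 with it (Monte Carlo error about .001). At r = 0, adding age moves power from .872 to .870 at EOT and from .868 to .866 for the average.

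**Cause.** In a separate simulation of the visit average (20,000 trials per setting), age explained 10% or 20% of residual variance. Without an age term, type I error was .042 and .038 under stratified randomization, but .050 and .049 under unstratified randomization. The conservatism therefore comes from stratifying on age and then omitting it. At 5% and 20%, which correspond to r = .2 and .4 here (r²/.8), continuous age raised power from .862 to .874 and from .874 to .920. These gains agree with the table.

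**Group-by-time.** With complete data, an age main effect leaves the interaction estimate unchanged. With 2 of 180 visits missing (about 1%; the plan reports that "to date <1% of data in our preliminary studies are missing"), the estimate moved by at most 0.041 SE.

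**Imbalance rule.** At an assumed threshold of .25 SD, age would qualify in 12 to 13% of stratified trials, against 34% without stratification. At .5 SD the figures are 0.2% and 5.4%.

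**The case against.** The strongest objection is that the effect may not touch the deciding test. Data analysis lists baseline among the times at which groups are compared, the Aim 1 hypothesis concerns improvement, and the power section is framed around increases. If baseline is treated as a response and the treatment test is the group-by-time contrast from baseline to EOT, an age main effect changes nothing. A four-visit fit at r = .4 showed a standard-error ratio of 1.0000. This stands, and it limits the point to group differences at a visit or averaged over visits. It does not remove the point. The same section also enters baseline as a covariate and speaks of estimating the group effect, and the sample size is framed around group differences at EOT.

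Three further objections are fair. The size depends on a correlation that the documents do not supply; choosing age as a stratification factor suggests that the sponsor thinks it matters, but not how much. The error is in the safe direction, so no false positive can follow. The power gains are computed at an effect chosen to give about .87. They are not gains at the stated 4.25-point difference with SD of about 10, which is d = .425 and gives power of about .38 (normal approximation) in a single-visit comparison.

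The covariate rule is only partial mitigation, because it is optional and is rarely met for a stratified factor.

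**Conclusion.** The concern holds and is minor. Age is used in the randomization and absent from the specified models. If age is prognostic given baseline, the standard error of the group difference at a visit or averaged over visits is overstated and its test is slightly conservative. Over the assumed r of .2 to .4, including age is worth 0.8 to 3.6 points of power at EOT and 1.0 to 4.8 points for the visit average. The group estimate is unbiased either way. If age is not prognostic, or if group-by-time is the deciding test, there is nothing to gain.

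The direction follows from the design. The size rests on the assumed correlations, strata and block size. With visit correlations of .6 and .8, the EOT standard-error ratios were unchanged. For the average they were 1.025, 1.063, 1.120 at .6 and 1.021, 1.053, 1.102 at .8.

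**What to change.** In Analysis of Motor Outcomes (Aim 1), pre-specify age at randomization as a continuous linear fixed effect in the ARAT, FMA and WMFT models, beside the outcome's baseline value. Add the baseline-function stratum only for outcomes whose own baseline is a different measure from the one used to stratify. Fix the covariates of the primary models before outcome data are analysed, and keep covariates chosen for observed imbalance to sensitivity analyses.

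The cost is a change of wording. Age is already collected, and the term uses one degree of freedom among 60 participants. If age turns out not to be prognostic, the loss is about 0.2 to 0.3 points of power.
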